Patients with end-stage liver disease (ESLD) have poor physical fitness and muscle wasting (sarcopenia). Both conditions have been associated with elevated mortality before and after liver transplantation (LT). Limited data have shown that exercise benefits patients with chronic liver disease/cirrhosis, however, there are no studies with ESLD patients potentially eligible for LT. Effectively improving physical fitness and sarcopenia in ESLD should positively impact clinical outcomes before/after LT. The primary aim of this study is to improve both physical fitness and sarcopenia in ESLD patients through a 12-week physical training program. Secondary aims will focus on changes in anthropometrics, body composition, quality of life, and metabolic profile. This is a randomized clinical trial including 50 patients, with half allocated to the active group (physical training program) and half to standard of care. Physical training program will consist on achieving $\geq 10,000$ steps/day with an increase of ≥ 4000 above the baseline, facilitated by the feedback from daily step counts and behavioral modification therapy (favoring change towards a more active lifestyle). All participants will have to wear a pedometer bracelet (Fitbit) throughout duration of study (reads blinded to controls), and will receive a daily essential amino acid (EAA) supplement containing approximately 2.25 g of L-leucine along with nutritional consultation. Cardiorespiratory exercise test (CRET), 6-minute walk test (6MWT), and abdominal CT scan will be performed in all participants before and after the period of study to assess for physical fitness and sarcopenia. Anthropometrics, bioelectrical impedance, whole-body DEXA scan, sickness impact profile questionnaire, and the metabolic profile will be obtained at baseline and after completion of the study as well. Blood EAA levels, myostatin, and insulin-related growth factor-1 will be determined at baseline, and at week 12 of study. Durability of changes 6 months post-LT will be assessed as well, when applicable.

INTRODUCTION

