Pattullo *et al* included 16 patients with chronic hepatitis C - 6 of whom were cirrhotic - in a 24-week exercise and dietary program. Exercise consisted on walking and patients were encouraged to increase their daily step count using a pedometer to self-monitor their progress. With the aid of behavior modification therapy we were able to increase daily step counts from a baseline of 6853 (2440-9533) to 10967 (7959-13566) steps/day, and there were significant improvements in fasting glucose, insulin resistance (HOMA-IR (3.6 [2.8-4.9] to 2.1 [1.8-3.6])), BMI (36 [31-38] to 31 [29-36]), waist circumference, fatigue and mood scores. These changes were paralleled by significant drops in ALT, AST, and GGT levels, and by increased adiponectin, and decreased leptin. Calorie restriction had a median of 33% during the intervention.(5) In a total of 8 patients with cirrhosis initially included in this study, we could observe an improvement in quality of life as well, reflected by the physical component summary of SF36 (specifically on physical function, bodily pain, and vitality).(24) With a similar design, Konishi *et al*, were able to demonstrate that in 16 patients with chronic hepatitis C, an increase in daily step counts from around 5500 to over 7000 during a period of 6 months had a positive impact in insulin resistance (HOMA-IR), BMI, waist circumference, ALT, and leptin levels. Of note, this study provided standardized nutritional counseling, but no changes in caloric intake were noted.(4) In a randomized clinical trial, Soriano *et al* showed that a period of 12 weeks of supervised moderate exercise thrice-weekly plus 10 g/d of oral leucine (n=8) caused an increase in albumin levels, muscle mass (as reflected by the thigh circumference), cardiorespiratory endurance (6MWT increased from 321 ± 36 to 417 ± 33 m), and quality of life (according to SF36). None of these changes were noted in the control group (n=9).(25) We recently completed a randomized clinical trial consisting of 12 weeks of a supervised physical training program in patients with cirrhosis. Out of 23 patients included, 11 were allocated to moderate exercise/kinesiotherapy for about 70 minutes per session, three times per week, at a cardiac rehabilitation center. Remaining patients continued with standard of care. Phase angle (PhA) from bioelectrical impedance was used to evaluate muscle mass. We showed a trend for improved muscle mass in the exercise group, as PhA improved in 63% of patients compared to 25% of the control group ($p=0.10$).

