We currently spend great resources into avoiding substance abuse relapse and improving patient's compliance during the LT evaluation, but have omitted education regarding healthy lifestyle habits including physical activity and exercise, what might bring enormous benefits to LT worldwide. For patients with cirrhosis and ESLD, the period before liver transplantation is full of self-reflection and insight, education, and lifestyle changes. These behavioral tuning has allowed keeping the rate of alcohol recidivism at no more than 10% in most transplant centers, and a low prevalence for the use of tobacco products after LT. It is expected that any recommendation or prescription regarding physical activity would have greater acceptance and a more durable effect if properly administered once patients have reached ESLD, or while they are being evaluated for LT, as they become very receptive to make changes in their lifestyle as far as it helps to facilitate transplant candidacy. However, unlike diabetes mellitus and cardiac diseases, it is unknown for ESLD patients what the mode, intensity, and duration of exercise that will provide improved outcomes are. More importantly, there is a lack of knowledge regarding the safety of exercise with respect to hyperammonemia and occurrence of HE.

SPECIFIC AIMS

The primary aims of current study are to:

- Improve the physical fitness of patients with ESLD whom are potentially eligible for liver transplantation with a 12-week physical training program.
 - The hypothesis is that only patients enrolled in the active arm will improve their physical fitness, as determined by cardiorespiratory stress test and 6-minute walk test.
- Improve sarcopenia in patients with ESLD whom are potentially eligible for liver transplantation with a 12-week physical training program
 - The hypothesis is that only patients enrolled in the active arm will show an increase in the skeletal muscle area, as determined by CT-scan.

As secondary aims, this 12-week training program will look into:

- The changes in the ammonia and anaerobic/lactate thresholds at the end of the study for each group.
 - It is expected to find increased ammonia and anaerobic/lactate thresholds in the active arm, when compared to the control arm.
- The changes in anthropometrics (weight, BMI, waist circumference), and body composition at the end of the study for each group.

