 - It is expected to find improved anthropometrics, decreased fatty mass, and increased fat-free mass in the active arm, when compared to the control arm.
- The changes in quality of life at the end of the study for each group.
 - It is expected to find improvements in quality of life in the active arm, when compared to the control arm.
- Safety of the physical training program, by systematically documenting episodes of variceal bleeding, and hepatic encephalopathy.
 - No increased risk for complications such as GI bleeding and encephalopathy is expected for the active arm with current research design.
- The changes in the metabolic profile (fasting glucose, fasting insulin, lipid profile (total cholesterol, LDL-cholesterol, HDL-cholesterol, triglycerides) at the end of the study for each group.
 - It is expected to have an improved metabolic profile in the active arm, when compared to the control arm.
- The changes in myostatin and insulin-related growth factor 1 (IGF-1) before and after 12 weeks of study.
- In patients undergoing liver transplantation, extension of training program benefits 6 months after liver transplant (reassessment of physical fitness, sarcopenia, anthropometrics, body composition, and metabolic profile).
 - Durability of the beneficial benefits of the training program will be expected across all evaluated variables, with no changes in the control arm after transplant.

RESEARCH STRATEGY

Significance

Unlike other chronic diseases (*i.e.* diabetes mellitus), there are no recommendations for physical training and exercise in patients with cirrhosis. This derives from the fact that there is a paucity of data on the physiologic effects of exercise in patients with cirrhosis and portal hypertension, as well as on the benefits that such training can bring in the long term. Moreover, some safety concerns have been raised in the past particularly with regards to an increased risk for variceal bleeding and HE. Apart from a few pilot studies using supervised exercise as an intervention there are no clinical trials addressing the benefits of an exercise program in patients with ESLD. Furthermore, no study has looked into how a training program can translate into benefits after LT, and since LT patients have a very high risk for metabolic and cardiovascular disease, such a study is highly awaited.

Innovation

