The study will occur over a total of 14 weeks, although duration of the intervention will consist of 12 weeks. The first two weeks will serve the purpose of identifying the baseline physical activity of each participant. During the second week all baseline studies/determinations will be completed, with randomization occurring by the end of week 2. Allocation will be stratified by presence or absence of refractory ascites.

Follow up visits for behavioral therapy will occur every 2 weeks for the first 8 weeks, and then on a 4-weekly basis (only active group). Nutritional consultation will occur every 2 to 4 weeks throughout the study (both active and control group). During each visit, the EAA supplement jar will be inspected for percent emptiness (in analogy to a pill count) in order to quantify adherence. Bi-weekly phone calls will be made to all subjects to enhance adherence to recommendations. Standard of care investigations (blood chemistries, hematology and coagulation, liver function tests, etc.) will be ordered according to the needs of the patient and the criteria of the investigator or responsible clinician. Clinical status and complications from portal hypertension, particularly variceal bleeding and HE, will be systematically investigated on each visit.

Research Tests - Variables to Measure

Prior to randomization each subject will be scheduled to undergo all baseline investigations, as follows (see Research Calendar below):

Cardiorespiratory stress test (CRET) and anaerobic threshold (Week -1, Day 1)

CRET will be performed early in the morning on a fasting state, following the maximal incremental cycle ergometry protocol from our Pulmonary Physiology Laboratory, and in agreement with the American Thoracic Society.(38) Briefly, test consists on having the patient on a cycle ergometer performing a progressively increasing work rate until reaching: volitional exhaustion, or termination by the medical monitor. The Borg Rating of Perceived Exertion Scale will be used to help titrate intensity of work rate (aiming for a level of 13 to 17). Gas exchange measurement for

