The questionnaire Sickness Impact Profile (SIP) will be used to assess changes in the quality of life. Recent evidence suggests SIP to be superior to SF-36 in detecting health-related quality of life changes occurring in patients with ESLD. Metabolic profile will include determinations of fasting glucose, insulin (in subjects without diabetes mellitus), lipid profile (triglycerides, total-cholesterol, HDL-cholesterol, LDL-cholesterol), and HbA1c. Both SIP and the metabolic profile will be repeated after completion of the study period (12 weeks). The metabolic profile will be repeated 6 months after LT as well.

Randomization

Each participant will be randomly assigned to the active (physical activity + behavioral therapy + nutritional intervention) or control (nutritional intervention) group. The random allocation sequence will be generated using computer-generated random numbers. There will be no stratification in the randomization process, and allocation will be concealed.

Statistical analysis

Subjects sample has been defined by convenience, as there is no precedent for sample estimation. Descriptive statistics will include mean \pm SD and/or median (range), according to distribution of data. Shapiro-Wilk test will be used to assess normal distribution. Results on VCO₂ will be plotted against VO₂, whereas lactate, and ammonia will be plotted against VO_{2max}, for all patients as an aggregate. The lines determining the anaerobic, lactate, and ammonia thresholds will be calculated by linear regression. Continuous variables comparisons within groups will be done with paired t-test or Wilcoxon, whereas between groups will be done with t-test or Mann-Whitney. Categoric variables will be compared with chi-square or Fisher's exact test, as appropriate. Agreement between methods used to address body composition, bioelectrical impedance and DXA, will be investigated with Bland-Altman test.

Data collection and handling

Title: A physical activity program in end-stage liver disease
PI: [name]

Apart from the data generated by the study demographics and clinical information to properly classify the hepatic functional and cardiorespiratory status of each participant will be retrieved from the electronic medical record (EMR). Such information will include results from standard of care laboratories, imaging, and other special studies (EGD, pulmonary function tests, echocardiogram), to calculate MELD score, and Child-Turcotte-Pugh scores.

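### The plan does not say whether between-arm tests use week-12 values or change, plans no baseline-adjusted analysis, and does not make the between-arm comparison decisive for the primary aims.

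*Combined protocol and SAP*

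**What the plan says.** The Statistical analysis section gives one sentence for all continuous outcomes: "Continuous variables comparisons within groups will be done with paired t-test or Wilcoxon, whereas between groups will be done with t-test or Mann-Whitney". The variable entering the between-arm test is not named. The only regression planned is for the anaerobic, lactate and ammonia threshold lines, and no covariate-adjusted comparison of the arms appears anywhere.

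The baseline data exist for every participant. The opening summary says "Cardiorespiratory exercise test (CRET), 6-minute walk test (6MWT), and abdominal CT scan will be performed in all participants before and after" the study period, and the section on research tests says "Prior to randomization each subject will be scheduled to undergo all baseline investigations".

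Under Specific Aims, the primary hypotheses are that "only patients enrolled in the active arm will improve their physical fitness, as determined by cardiorespiratory stress test and 6-minute walk test" and that "only patients enrolled in the active arm will show an increase in the skeletal muscle area, as determined by CT-scan". Most secondary expectations are worded as comparisons of the arms, for example "It is expected to find increased ammonia and anaerobic/lactate thresholds in the active arm, when compared to the control arm". Several secondary aims are framed as changes, for example "The changes in quality of life at the end of the study for each group".

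The Statistical analysis section also states that the sample size is a convenience figure. The summary gives 50 patients, half to each arm.

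**The concern.** Three things are left open.

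1. **The tested variable.** A t-test on week-12 values and a t-test on change are different analyses with different power. The choice should not wait until the data are seen.
2. **Baseline adjustment.** The baseline value of each primary measure is collected anyway. Leaving it out of a model gives up precision for no saving, in a trial whose size was not chosen to give any stated power.
3. **The decisive comparison.** A hypothesis that only one arm improves can be read as two separate within-arm tests: one significant, one not. That pattern is not a test of the difference between arms. If both arms gained equally, it could appear by chance and be taken for a training effect.

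**Working it through.** **Inputs from the documents.** 50 patients, half per arm, so n = 25 (summary). No alpha, power, effect size, SD or dropout rate is given, so there is no sample-size figure to reproduce.

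**Assumptions.** Two-sided 5%, complete follow-up, normal data, equal SD (set to 1) at both times, and a true difference of 0.6 SD of the value. The baseline-to-week-12 correlation r is not in the documents, so 0.5, 0.7 and 0.9 are shown.

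**Step 1: effective SD under each analysis.**
- Week-12 values: 1
- Change: √(2(1 − r))
- ANCOVA on baseline: √(1 − r²)

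The standardised effect is 0.6 divided by the effective SD, and the noncentrality is that effect × √(25/2).

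| r | SD, change | SD, ANCOVA | Noncentrality: week-12 | Noncentrality: change | Noncentrality: ANCOVA |
|---|---|---|---|---|---|
| 0.5 | 1.000 | 0.866 | 2.12 | 2.12 | 2.45 |
| 0.7 | 0.775 | 0.714 | 2.12 | 2.74 | 2.97 |
| 0.9 | 0.447 | 0.436 | 2.12 | 4.74 | 4.87 |

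**Step 2: power.** Noncentral t with 48 degrees of freedom for the first two analyses. ANCOVA by simulation, which allows for chance baseline imbalance; the noncentral t with 47 degrees of freedom gives 67%, 83% and over 99%.

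| r | Week-12 values | Change | ANCOVA |
|---|---|---|---|
| 0.5 | 55% | 55% | 66% |
| 0.7 | 55% | 77% | 82% |
| 0.9 | 55% | over 99% | over 99% |

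Against change, ANCOVA gains about 11, 5 and 0 percentage points, and its 95% confidence interval is about 12%, 7% and 1.5% narrower. Against week-12 values it gains about 11, 27 and 45 points. At r = 0.7 and 0.9 the unnamed variable therefore matters more than the choice between change and ANCOVA.

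**Step 3: what would follow if the paired tests decided.** Suppose there is no training effect and both arms have the same true change, in units of the SD of change. Let p be the chance that one arm's paired t-test (n = 25) shows a significant improvement. The chance that the active arm is significant and the control arm is not is p(1 − p).

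| Shared true change | p | p(1 − p) |
|---|---|---|
| 0 | 0.025 | 2.4% |
| 0.2 SD | 0.159 | 13% |
| 0.4 SD | 0.484 | 25% |
| 0.6 SD | 0.821 | 15% |

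These are per measure. Since p(1 − p) cannot exceed 0.25, 25% is the ceiling. A two-sample test would wrongly favour the active arm 2.5% of the time at any shared change.

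**Step 4: how the team has compared arms before.** The Introduction says of its earlier trial (23 patients, 11 to exercise) that "PhA improved in 63% of patients compared to 25% of the control group", with p = 0.10. Counts of 7 of 11 and 3 of 12 fit those percentages and give Fisher's exact p = 0.0995. That precedent is a between-arm test of improvement from baseline.

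**The case against.** A reader might infer that the between-arm tests ignore the baseline values altogether. The documents do not support that. A t-test or Mann-Whitney on change fits the planned sentence and uses every baseline value. The secondary aims speak of changes, and the earlier trial compared changes between arms (HVPG and phase angle). What stands is that the variable is unnamed.

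A reader might also infer that the primary aims will be decided by the paired tests. No section says so. A between-arm test is planned, and the earlier trial was reported that way. The 25% figure needs a paired-test rule, no training effect and a shared gain near 0.4 SD. A shared gain is possible, because both arms receive nutritional support intended to help muscle. A shared decline is possible too, since the Introduction says fitness worsens as liver failure advances. With no shared change the figure is 2.4%. What stands is that the decisive comparison is not named.

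It can also be said that ANCOVA is a preference: the planned test controls error, the correlation is unknown, and the Innovation section presents the results as preliminary to a multicentre trial. The first two points are correct and limit the claim to precision. The third does not remove it, since a narrower interval is also useful for planning the next trial.

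**Conclusion.** The point holds as a matter of precision and clarity, not of validity. The plan leaves the between-arm variable unnamed, includes no baseline-adjusted analysis, and does not say which comparison decides the primary aims.

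Under the assumptions above, the loss relative to ANCOVA is modest if change is tested (about 11 points of power at r = 0.5, 5 at r = 0.7, negligible near 0.9). It is larger if week-12 values are tested (about 11, 27 and 45 points). These sizes depend on an assumed effect and correlation, and on complete follow-up.

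The false active-arm-only pattern (13% at a shared gain of 0.2 SD of change, 25% at 0.4 SD) is conditional on a decision rule that the documents do not state. It is a reason to name the rule, not evidence that the trial will use the wrong one. The point should be fixed, and the confidence is high.

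**What to change.** - State both primary hypotheses as between-arm differences at week 12.
- For VO2max, 6MWT and L3 muscle area, make the decisive analysis an ANCOVA of the week-12 value on arm and baseline value, by randomised group, reporting the adjusted difference with its 95% confidence interval.
- Apply the plan's Shapiro-Wilk check to the model residuals. If they are clearly non-normal, use a rank version and show the unranked estimate beside it, because ranks give no difference in original units.
- Label the within-arm paired tests descriptive.
- Reconcile the Follow Up section, which stratifies allocation by refractory ascites, with the Randomization section, which says there is no stratification. Add refractory ascites to the model if allocation was stratified by it.

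**Cost.** Wording only, using data already collected: one degree of freedom for the baseline value, and a second if refractory ascites is included. Little is gained if the correlation is near 0.9.

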The 6MWT will be performed in agreement with the recommendations of the American Thoracic Society.(39) In brief, the test will be done indoors, along a long and flat enclosed corridor, aiming for as many laps (100 ft per half-lap) as possible, while patient is wearing a pulse oximeter. The investigator applying the test will use a stopwatch and write down heart rate and oxygenation, at baseline, and every minute until reaching a total of six minutes. The Modified Borg Scale will be used to rate shortness of breath and fatigue before and after the test. This test will be repeated after completion of the study period (12 weeks), and 6 months after LT.

Sarcopenia (abdomen CT-scan) (Week -1, Day 3)

A noncontrasted abdominal CT-scan will be used to measure the cross-sectional area of skeletal muscle at the level of the third lumbar vertebrae (L3). Images will be analyzed with SliceOmatic 4.3 (Tomovision, Montreal, Canada) measuring the cross-sectional area of skeletal muscle at this level (*i.e. psoas, paraspinals, quadratus lumborum, transversus abdominis, rectus abdominis, and internal and external obliques*). Muscle areas will be analyzed by an operator trained in musculoskeletal anatomy with tissue-specific Hounsfield unit thresholds (-29 to +150).(16) The L3 skeletal muscle area will be normalized to stature by the division of the muscle area by the height squared. Sarcopenia will be defined as a reduction in the L3 area of muscle mass $\leq 52.4 \text{ cm}^2/\text{m}^2$ in males and $\leq 38.5 \text{ cm}^2/\text{m}^2$ in females. This test will be repeated after completion of the study period (12 weeks), and 6 months after LT.

Nutritional consultation, anthropometrics, and body composition (Week -2, Day 3)

A dietitian or designated investigator will evaluate anthropometrics (weight, height, waist circumference), bioelectrical impedance, and whole-body dual energy X-ray absorptiometry scan (DXA). Bioelectrical impedance will be performed according to the manufacturer's recommendations: after overnight fasting, with subject in supine position with arms and legs abducted from the body, and source and sensor electrodes placed on the dorsum of both hand and foot on the right side of the body, respectively. After obtaining resistance (R), reactance (Xc)

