A database will be created to accumulate all of the clinical information generated during this study. No identifiers, apart from name and DOB, will be collected. All data will be stored in databases kept in a study folder created at PI's computer (password-protected). Main database will include aforementioned identifiers, however, each subject will have a unique study ID assigned, and once an analytic table is created, all PHI will be removed from the table (after approval by the PI). Only this de-identified dataset with unique study ID's will be used for statistical analyses. Therefore, the risk to the privacy of the individuals will be minimized.

The access to the research folder and its contents will be restricted to the research staffs listed in this submission form. The PHI will be kept in the main database until completion of the study. The main database containing PHI will be kept in the study folder and will be never transferred out without de-identification of the data. No hard copy research data will be generated in this project.

In order to quantify the muscle mass at the level of L3, electronic copies of abdomen CT-scans with no identifiers will be shared with [name] from the University of Alberta, in Canada. After proper quantification an analytic table including unique study ID's will be sent back to UAMS for integration into the main database.

Risks and Benefits

CRET is a safe procedure and the risk for having a complication, such as an acute coronary syndrome is mostly related to underlying chronic disease. The risk of death varies as well, from 1 death in 20,000 - 70,000 tests, depending mostly on the presence of underlying heart disease. In cohorts including healthy subjects, no deaths or major complications have been observed. Since LT candidates have to undergo a thorough cardiopulmonary evaluation and patients with any moderate to severe cardiopulmonary condition are not considered transplant candidates the risks for any major complication or death in this study should equal zero. Moreover, the personnel taking care of CRET constantly monitors physiologic responses to exercise (including electrocardiogram monitoring), and are trained to stop the test whenever there are signs for an impending complications, and can immediately and effectively perform cardiac resuscitation.

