Unlike CRET, in the 6MWT each patient determines the intensity of their exercise according to symptoms and cardiorespiratory fitness. The 6MWT is thus considered a very safe procedure, and it has been performed (without electrocardiogram monitoring) in thousands of older persons and thousands of patients with heart failure or cardiomyopathy without serious adverse events. Although patients with cardiopulmonary disease may be at increased risk for arrhythmias or cardiovascular collapse during testing, it is very unlikely for a complication to be witnessed given the selection criteria followed during LT evaluation (as above).

The risks associated with placement of an IV catheter and blood collection from a vein are minor bleeding, bruising, infection (a small risk any time the skin is broken), or needing more than one attempt to locate veins.

Both CT and DXA scans are associated with exposure to small amounts of ionizing radiation. The abdominal CT-scan will be restricted to a simple phase (non-contrasted) in order to limit radiation exposure, and thus it should not exceed 10 mSv. Since the initial CT-scan is performed as part

Title: A physical activity program in end-stage liver disease
PI: [name]

of the LT evaluation (standard of care), the study will derive in radiation exposure of approximately 20 mSv. This is a very low radiation exposure that might be associated with a low additional increase in lifetime risk for cancer (1 in 1000 to 10,000). In the case of DXA, exposure per whole-body scan is similar to daily background natural radiation exposure (0.01 mSv).

The electrical current used in bioelectrical impedance is very small and thus unlikely to stimulate electrically excitable tissues, particularly cardiac and nervous tissues. Moreover, there are no reports of untoward effects among thousands of individuals in whom bioelectrical impedance analysis has been performed. Actually, the currents employed are very small and below the threshold of perception.

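### The research CT scans are described as abdominal scans of up to 10 mSv with no stated range, although the only CT measurement planned is muscle area at L3

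*Combined protocol and SAP*

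**What the plan says.** The sarcopenia test under Research Tests - Variables to Measure reads: "A noncontrasted abdominal CT-scan will be used to measure the cross-sectional area of skeletal muscle at the level of the third lumbar vertebrae (L3". The single result taken from the images is then indexed to height: "The L3 skeletal muscle area will be normalized to stature by the division of the muscle area by the height squared". On repetition, the same section says: "This test will be repeated after completion of the study period (12 weeks), and 6 months after LT". The opening summary makes the post-transplant assessment conditional: "Durability of changes 6 months post-LT will be assessed as well, when applicable".

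Data collection and handling gives the same purpose for the images sent to the outside reader: "In order to quantify the muscle mass at the level of L3, electronic copies of abdomen CT-scans with no identifiers".

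On dose, Risks and Benefits states: "The abdominal CT-scan will be restricted to a simple phase (non-contrasted) in order to limit radiation exposure". It puts a ceiling of 10 mSv on the scan, treats the initial CT as standard of care within the transplant evaluation, and concludes that "the study will derive in radiation exposure of approximately 20 mSv". It describes this as very low and quotes an added lifetime cancer risk of 1 in 1000 to 10,000.

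No section gives a scan length or an upper and lower anatomical limit.

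**The concern.** The protocol sets out to limit radiation but restricts only the number of phases. When one vertebral level is measured, scan length is the other obvious limit, and nothing is said about it. No justification for wider coverage is offered, and no other part of the images is assigned a use.

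The week 12 and post-transplant scans are research exposure by the protocol's own account. If they are acquired as ordinary abdominal CTs, participants receive radiation that serves no planned measurement. What is at stake is avoidable participant burden. The point does not concern bias in the L3 measure, power or interpretability.

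**Working it through.** **1. What the CT is used for.** Setting the sections side by side:

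- Specific Aims: the sarcopenia hypothesis concerns skeletal muscle area by CT. It does not name L3.
- Sarcopenia test description: area at L3, divided by height squared, with sex-specific cut-offs.
- Data collection and handling: images go to the outside reader to quantify muscle at L3.
- Anthropometrics and body composition: bioimpedance and DXA are used, not CT.
- Statistical analysis: no further CT variable is named.

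So L3 muscle area is the only planned CT measurement.

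**2. The protocol's exposure figure.** Inputs from Risks and Benefits and the test description: at most 10 mSv per scan; two repeat scans; initial scan not counted.

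- Research exposure = number of research scans × dose per scan = 2 × 10 = 20 mSv. The stated figure is reproduced. DXA, at 0.01 mSv per scan, is negligible.
- Not transplanted: 1 × 10 = 10 mSv.
- If the baseline CT is also done only for research, add 10 mSv: up to 20 mSv if not transplanted and up to 30 mSv if transplanted.

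**3. What a limited range would leave.** The protocol gives no lengths, so these are assumptions: dose proportional to scanned length; abdominal scan 25-45 cm; block at L3 5-10 cm including margin.

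Dose kept per scan = 10 mSv × block length / scan length.

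| Block | Scan | Per scan | Two scans | Saving |
|---|---|---|---|---|
| 5 cm | 45 cm | 10 × 5/45 = 1.1 mSv | 2.2 mSv | 89% |
| 5 cm | 25 cm | 10 × 5/25 = 2.0 mSv | 4.0 mSv | 80% |
| 10 cm | 45 cm | 10 × 10/45 = 2.2 mSv | 4.4 mSv | 78% |
| 10 cm | 25 cm | 10 × 10/25 = 4.0 mSv | 8.0 mSv | 60% |

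The saving is therefore 6.0-8.9 mSv for one scan and 12.0-17.8 mSv for two, before the scout image.

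**4. Sensitivity.** With scans of 20-45 cm and a tighter block of 0.5-5 cm, the saving is 75% (1 − 5/20) to 99% (1 − 0.5/45). Pairing the shortest scan with the widest block gives 50% (1 − 10/20). Because 10 mSv is a ceiling, a lower actual dose reduces the saving in mSv in proportion but leaves the percentage unchanged.

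**The case against.** The strongest reply is that whole-abdomen coverage is inferred. A reader might take the protocol to prescribe it, but the text says only abdominal CT, and 10 mSv is an upper bound. A local practice of scanning a short range at L3 cannot be excluded. This stands: the documented fact is that the range is unstated. If the practice is already limited, the protocol should say so and the exposure figure should be revisited.

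The percentages also rest wholly on assumed lengths and are illustrative. A reader might further infer that every participant receives 20 mSv. The documents do not support that, since the second repeat scan applies only after transplantation.

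It is also tempting to say that a shorter scan changes nothing in the sarcopenia measure. That is too strong. L3 would have to be located on a scout image; if the block is mis-centred, the outside reader cannot recover the level, and a primary-aim value is lost or the scan repeated. The baseline may be a standard-of-care scan whose settings the protocol does not specify, so exact matching cannot be guaranteed. These are real but small costs, and a generous margin reduces the main one. The same acquisition rule would apply in both arms, so no difference between arms is expected from it.

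Finally, the absolute risk quoted is small, the dose is disclosed, and ethics approval and consent are required. That bears on priority. It does not supply a use for the exposure outside L3.

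**Conclusion.** The point holds in a limited form. The repeat CTs are described as non-contrast abdominal scans of up to 10 mSv with no limit on range, while only L3 muscle area is measured. On the plain reading, much of the research exposure yields no trial data. The ceiling is 10 mSv for non-transplanted and about 20 mSv for transplanted participants, provided the baseline scan is standard of care.

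A saving of roughly 60-89% follows if dose is proportional to length, the scan is 25-45 cm and the block 5-10 cm. None of these three is in the documents.

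The standard-of-care premise also needs care. The Approach section recruits from hepatology clinics as well as transplant referrals, and the CT is listed among the baseline study investigations, so some baseline scans might be done only for research. The documents do not establish that any will be.

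This is a worthwhile, inexpensive reduction in participant exposure. It is not a flaw in the endpoint or the analysis.

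**What to change.** In the sarcopenia test description and in Risks and Benefits:

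- State that any CT done only for research is a non-contrast acquisition limited to a block centred on L3. This covers week 12, 6 months after transplant, and any baseline CT not already obtained as standard of care.
- State that the block is located on the scout image, with a margin wide enough to guarantee the L3 level.
- Match acquisition settings to the participant's own baseline scan where feasible.
- Restate the exposure and cancer-risk sentences separately for transplanted and non-transplanted participants, using the dose radiology expects for the limited range.

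If full abdominal coverage is wanted for a reason not given in the protocol, state that reason instead.

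The cost is protocol wording and an instruction to radiology; no extra staff, procedures or patients are needed. The downsides are a small risk that a mis-centred block loses the L3 slice, which the margin reduces, and no full-abdomen images for unplanned use.
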